SDTM	study data tabulation model
T2DM	type 2 diabetes mellitus
TB	total bilirubin
TC	total cholesterol
TEAE	treatment-emergent adverse event
TG	triglycerides
ULN	upper limit of normal
US	United States
WBC	white blood cell
WHO	World Health Organization

[REDACTED]

[REDACTED]

[REDACTED]

[REDACTED]

Version Number:
Version Date:

0.5
14June2018

1. INTRODUCTION

This document describes the rules and conventions to be used in the presentation and analysis of efficacy and safety data for Protocol 1002-047. It describes the data to be summarized and analyzed, including specifics of the statistical analysis to be performed.

This statistical analysis plan (SAP) is based on the final protocol version dated September 22, 2016 and amendment 1 dated 18 January 2017, amendment 2 dated 22 March 2017, and amendment 3 dated 09 May 2017.

2. STUDY OBJECTIVES

2.1. PRIMARY OBJECTIVE

The primary objective is to assess the 12-week efficacy of bempedoic acid 180 mg/day versus placebo in decreasing low-density lipoprotein cholesterol (LDL-C) in high cardiovascular (CV) risk patients with hyperlipidemia (with underlying heterozygous familial hypercholesterolemia [HeFH] and/or atherosclerotic cardiovascular diseases [ASCVD]) who are not adequately controlled with their maximally tolerated lipid-modifying therapy.

2.2. SECONDARY OBJECTIVES

The secondary objectives are:

- To evaluate the effect of 24-week treatment with bempedoic acid 180 mg/day versus placebo on LDL-C.
- To evaluate the effect of bempedoic acid 180 mg/day versus placebo on non-high-density lipoprotein cholesterol (non-HDL-C), total cholesterol (TC), high-sensitivity C-reactive protein (hsCRP), and apolipoprotein B (apoB) after 12 weeks of treatment.

2.3. TERTIARY OBJECTIVES

The tertiary objectives are:

- To evaluate the long-term treatment (52 weeks) with bempedoic acid 180 mg/day versus placebo on LDL-C, non-HDL-C, TC, HDL-C, TG, hsCRP, and apoB.
- To evaluate the 52-week safety and tolerability of bempedoic acid 180 mg/day compared to placebo.

[figure not shown]
Statistical Analysis Plan

3. STUDY DESIGN

3.1. GENERAL DESCRIPTION

This is a Phase 3, long-term randomized, double-blind, placebo-controlled, parallel group, study evaluating the efficacy of bempedoic acid in high CV risk patients with hyperlipidemia (patients with underlying HeFH and/or ASCVD) who are not adequately treated with their maximally tolerated lipid-modifying therapy. The study will be conducted at approximately 125 clinical sites in North America and Europe. Screening Week -5 (Visit S1) will be approximately 5 weeks prior to randomization, but can be extended for an additional 4 weeks if needed to adjust background medical therapy or for other reasons as specified in the protocol. Eligible patients will return to the clinical site at Week -4 (Visit S2) to initiate administration of single-blind (patient only) placebo. Eligible patients will return at Week -1 (Visit S3) for lipid and safety laboratories and an assessment of tolerability and study drug adherence. Approximately 750 eligible patients will be randomized 2:1 on Day 1 (Visit T1) to receive either bempedoic acid 180 mg (n = 500), or placebo (n = 250) once daily for 52 weeks. Randomized patients will return for clinic visits at Week 4 (Visit T2), Week 12 (Visit T4), Week 24 (Visit T5), and Week 52 (Visit T7). A phone visit will occur at Week 8 (Visit T3) and Week 36 (Visit T6).

Table A: 1002-047 Study Design

3.2. SCHEDULE OF EVENTS

The schedule of events can be found in Appendix I of the protocol.

4. PLANNED ANALYSIS

The following analysis will be performed for this study:

- Analysis for Data Monitoring Committee (DMC) meetings
- Final Analysis

4.1. DATA MONITORING COMMITTEE (DMC)

The subset of outputs for the DMC is listed in [Appendix 3](#). Access to results will be provided by Quintiles in a separate unblinding plan.

4.2. FINAL ANALYSIS

All final, planned analysis identified in this SAP will be performed by IQVIA Biostatistics following Sponsor Authorization of this Statistical Analysis Plan, Database Lock, Sponsor Authorization of Analysis Sets and unblinding of Treatment.

5. ANALYSIS SETS

Agreement and authorization of subjects included/ excluded from each analysis set will be conducted prior to the unblinding of the study.

5.1. SAFETY ANALYSIS SET [SAF]

The Safety Analysis Set (SAF), used for all of the safety summaries, is defined as all randomized patients who received at least 1 dose of double-blind study medication. Patients in the SAF will be included in the treatment group that they actually received, regardless of their randomized treatment.

5.2. FULL ANALYSIS SET [FAS]

The Full Analysis Set (FAS), used for all of the efficacy analysis, is defined as all randomized patients. The FAS is also known as the intention-to-treat (ITT) set of patients. Patients in the FAS will be included in their randomized treatment group, regardless of the treatment they actually received.

5.3. PK ANALYSIS SET [PKS]

The PK Analysis Set will include all patients in the safety analysis set who have at least one non-missing PK assessment. These patients will be summarized for PK concentrations unless major protocol deviations are identified during the protocol deviation review or if key dosing or sampling information is missing.

6. GENERAL CONSIDERATIONS

6.1. REFERENCE START DATE AND STUDY DAY

Study Day will be calculated from the reference start date, and will be used to show start/ stop day of assessments and events.

Reference start date is defined as the day of the first dose of double-blind study medication (Day 1 is the day of the first dose of study medication. In case the first dose date is missing, the randomization date will be used instead.

If the date of the event is on or after the reference date then:

$$\text{Study Day} = (\text{date of event} - \text{reference date}) + 1.$$

If the date of the event is prior to the reference date then:

$$\text{Study Day} = (\text{date of event} - \text{reference date}).$$

In the situation where the event date is partial or missing, the date will appear partial or missing in the listings, and Study Day, and any corresponding durations will be presented based on the imputations specified in [Appendix 2](#); Partial Date Conventions.

6.2. BASELINE

Unless otherwise specified, baseline is defined as the last non-missing measurement taken on or prior to reference start date (including unscheduled assessments). In the case where the last non-missing measurement and the reference start date coincide, that measurement will be considered pre-baseline, but Adverse Events (AEs) and medications commencing on the reference start date will be considered post-baseline.

Baseline for calculated LDL-C, HDL-C, non-HDL-C, TG, and TC is defined as the mean of the values from Week -1 (Visit S3) and predose Day 1/Week 0 (Visit T1) (i.e., the last two non-missing values on or prior to Day 1). If only one value is available then that single value will be used as baseline.

Baseline for apoB and hsCRP is defined as the predose Day 1/Week 0 (Visit T1) value (i.e. the last non-

[REDACTED]
[REDACTED]

Statistical Analysis Plan

missing value on or prior to Day 1). If this is not available, then the last non-missing value prior to the first dose of double-blind study medication (including unscheduled assessments) will be used as baseline.

6.3. RETESTS, UNSCHEDULED VISITS AND EARLY TERMINATION DATA

In the event of a missing value at a scheduled visit, and if an unscheduled visit falls within the protocol-defined window of that visit (see table below), the value from the unscheduled visit will be used for that visit.

In the case of a retest (same visit number assigned), the later available measurement for that visit will be used for by-visit summaries.

Listings will include scheduled, unscheduled, retest and early discontinuation data.

6.4. VISIT WINDOWING

Protocol-defined assessments will be “slotted” to study weeks based on collection date and applying the rules summarized in the following table. If there is more than one scheduled visit in a visit window, the visit closest to the target date will be used. If there is a tie between the numbers of days from the target date, the visit after the target date will be used. Unscheduled visits that fall within the protocol-defined visit windows will be summarized in the by-visit analyses if there is no scheduled visit available. If there is more than one unscheduled visit within the protocol-defined visit window and no scheduled visit available, the unscheduled visit closest to the scheduled visit date will be used. If there is a tie between the numbers of days from the target date, the visit after the target date will be used.

However, exposure data obtained from the drug accountability and administration CRF will be summarized and listed according to nominal visit information.

Analysis Visit	S1	S2	S3	T1	T2	T3	T4	T5	T6	T7
Study Week	-5	-4	-1	week 0	4	8	12	24	36	52/EOS
Target Study Day	-35	-28	-7	1	29	57	85	168	252	365
Analysis Visit Windows	$[-\infty, -32]$	$[-31, -18]$	$[-17, -1]$	$[1, 1]$	$[2, 43]$	$[44, 71]$	$[72, 127]$	$[128, 211]$	$[212, 309]$	$[310, \infty]$

6.5. STATISTICAL TESTS

The default significance level will be (5%); confidence intervals will be 95% and all tests will be two-

sided, unless otherwise specified in the description of the analysis.

6.6. COMMON CALCULATIONS

For quantitative measurements, change from baseline will be calculated as:

- Test Value at Visit X – Baseline Value

Percent change from baseline will be calculated as:

- $[(\text{Test Value at Visit X} - \text{Baseline Value}) / \text{Baseline Value}] \times 100$

6.7. SOFTWARE VERSION

All analysis will be conducted using SAS version 9.4 or higher.

7. STATISTICAL CONSIDERATIONS

7.1. SAMPLE SIZE

The primary efficacy endpoint for this study is the percent change from baseline to Week 12 in LDL-C.

The sample size of 500 randomized patients in the bempedoic acid 180 mg group and 250 randomized patients in the placebo group is expected to provide more than 95% power to detect a difference of 15% in the percent change from baseline to Week 12 in LDL-C between the bempedoic acid treatment group and the placebo group. This calculation is based on a 2-sided t-test at the 5% level of significance ($\alpha = 0.05$) and a common standard deviation of 15%. The sample size of 500 randomized patients in the bempedoic acid 180 mg group and 250 randomized patients in the placebo group gives a total study sample size of 750.

7.2. ADJUSTMENTS FOR COVARIATES AND FACTORS TO BE INCLUDED IN ANALYSIS

The following covariates and factors are used in the analysis. For details of their inclusion in the models, see the specific analysis section.

- treatment group (bempedoic acid 180 mg/day; placebo)
- CV risk (ASCVD only; HeFH with or without ASCVD)
- baseline statin intensity (high intensity; moderate intensity; low intensity)
- baseline laboratory value of interest

- treatment by subgroup interaction term for subgroup analyses of efficacy variables

7.3. MULTICENTER STUDIES

This study will be conducted by multiple investigators at multiple centers in North America and Europe.

7.4. MISSING DATA

Missing efficacy data will be handled as described in section 15.1.2 of this analysis plan.

7.5. MULTIPLE COMPARISONS/ MULTIPLICITY

In terms of controlling the overall Type I error rate, a gatekeeping or stepdown approach will be used to test the primary efficacy endpoint and then specific secondary efficacy endpoints sequentially in order to preserve the study-wise Type I error rate. The sequence for the stepdown procedure in this study is as follows:

- Test the primary efficacy endpoint: percent change from baseline to Week 12 in LDL-C
- Test the percent change from baseline to Week 24 in LDL-C
- Test the percent change from baseline to Week 12 in non-HDL-C
- Test the percent change from baseline to Week 12 in TC
- Test the percent change from baseline to Week 12 in apoB
- Test the percent change from baseline to Week 12 in hsCRP

In this hierarchical testing structure, each hypothesis is tested at a significance level of 0.05, two-sided. Statistical significance at each step is required in order to test the next hypothesis. If the primary endpoint meets the criteria for statistical significance, then the percent change from baseline to Week 24 in LDL-C will be tested; and so forth.

8. OUTPUT PRESENTATIONS

[Appendix 1](#) shows conventions for presentation of data in outputs.

The templates provided with this SAP describe the presentations for this study and therefore the

format and content of the summary tables, figures and listings to be provided by IQVIA Biostatistics. Unless otherwise specified all outputs will be presented by randomized treatment group.

9. DISPOSITION AND WITHDRAWALS

All patients who were screened will be accounted for in this study. Reasons for screen failure will be summarized by pre-defined categories per CRF. For screen fail due to inclusion or exclusion criteria violation, the criteria category will be presented. Patient disposition and withdrawals (both from study treatment and the study) will be summarized for the FAS. The number of patients in each analysis set and by visit will be presented for all randomized patients.

10. PROTOCOL DEVIATIONS

All protocol deviations will be provided in a listing with type and description. Major protocol deviations will be summarized by treatment group. The protocol deviations are recorded and tracked in the trial monitoring platform CTMS. The final protocol deviations will be determined before treatment group is unblinded.

11. DEMOGRAPHIC AND OTHER BASELINE CHARACTERISTICS

Demographic data and other baseline characteristics will be summarized by treatment group for the FAS.

No statistical testing will be carried out for demographic or other baseline characteristics.

The following demographic and other baseline characteristics will be reported for this study:

- Age (years) - calculated relative to date of randomization
- Age category (<65 years vs. ≥65 years and < 75 years vs. ≥75 years)
- Gender
- Race
- Ethnicity
- Region (US vs. Canada vs. EU)
- Stratification factor
- CV risk (ASCVD only; HeFH (with or without ASCVD))
- Baseline statin intensity (high intensity; moderate intensity; low intensity)
- Weight (kg)

Statistical Analysis Plan

- Height (cm)
- BMI (kg/m²)
- BMI category (< 25 vs. 25 - < 30 vs. ≥ 30 kg/ m2)
- Baseline Laboratory Results (Total Cholesterol, LDL-C, HDL-C, Triglycerides, Non-HDL-C, Apolipoprotein B, and hsCRP)
- Baseline LDL-C category (<130 mg/dL, ≥130 and < 160 mg/dL, or ≥160 mg/dL)
- Baseline eGFR (normal: ≥90 mL/min/1.73m²; mild Renal Impairment: 60-89 mL/min/1.73m²; moderate Renal Impairment: 30-59 mL/min/1.73m², and severe Renal Impairment (15-29 mL/min/1.73m²)
- History of diabetes (Yes vs. No)
- History of hypertension (Yes vs. No)
- Baseline Vital Signs (systolic blood pressure (SBP) and diastolic blood pressure (DBP))
- Alcohol consumption (Non-Drinker, Former Drinker, or Current Drinker)
- Tobacco use (Never Used, Former User, or Current User)

11.1. DERIVATIONS

- Age (years) = (date of randomization – date of birth)/365.25
- BMI (kg/ m²) = weight (kg)/ height (m)²

12. MEDICAL AND SURGICAL HISTORY

Medical and Surgical History information will be presented by MedDRA SOC (System Organ Class) and PT (Preferred Term) for the FAS. Medical History conditions are defined as those conditions which started prior to signing the inform consent form (ICF) and stopped prior to or at screening. Medical History will be coded using MedDRA Version 20.1.

13. CONCOMITANT ILLNESSES

Concomitant Illnesses will be presented by SOC (System Organ Class) and PT (Preferred Term) for the FAS. Concomitant Illnesses are conditions (other than the indication being studied) which started prior to signing ICF and are ongoing at the date of randomization. Concomitant Illnesses will be coded using MedDRA Version 20.1

14. CARDIOVASCULAR HISTORY/RISK FACTORS

Cardiovascular history/risk factors collected at screening will be presented in a table by treatment group and data listing.

15. MEDICATIONS

Prior and concomitant medications will be presented for the SAF and coded using the September 2017 version of the World Health Organization Drug Dictionary Enhanced (WHO-DDE).

Medications will be summarized by ATC classification and preferred term by treatment group. Prior and concomitant lipid modifying therapy including statin, PCSK9i, ezetimibe and others will be tabulated and listed separately.

See [Appendix 2](#) for handling of partial dates for medications, in the case where it is not possible to define a medication as prior or concomitant to treatment, the medication will be classified by the worst case, i.e. concomitant.

Prior medications are medications which started and stopped prior to the first dose of double-blind study medication.

Concomitant medications are medications which: started prior to, on or after the first dose of double-blind study medication and started no later than 30 days following end of study medication, AND ended on or after the date of first dose of study medication or were ongoing at the end of the study.

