Each ANCOVA will be performed using the FAS, with patients included in their randomized treatment group regardless of the treatment they actually received. Same imputation method described for the primary endpoint will be used for those secondary endpoints included in the step-down procedure, while only observed data analysis will be used for other secondary and tertiary endpoints. For each lipid parameter and analysis time point, the LSM and SE will be provided for both treatment groups, along with the placebo-corrected LSM, its 95% CI and associated p-value.

The ANCOVA assumption of normality will be assessed. If non-normality of the data is found at any time point for any parameter, either the data will be transformed so that it is normally distributed or a nonparametric test will be considered instead of the planned ANCOVA.

Percent change from baseline to Week 24 and to Week 52 LDL-C will be analyzed similarly with patients in the FAS who did not receive additional lipid-lowering therapy by that time point (by Week 24 for the Week 24 analysis; by Week 52 for the Week 52 analysis) included in the analyses. Only observed case data will be used (no imputation for missing data). Output from each time point will include the LSM and SE for each treatment group, as well as the placebo-correct LSM, 95% CI, and p-value.

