15.2. ADDITIONAL POST-RANDOMIZATION ADJUNCTIVE TRIGLYCERIDE-LOWERING THERAPY

The number and percent of patients requiring additional (post-randomization) TG-lowering therapy (only when TG>1000) will be summarized by treatment group, ATC class 4 and medication name, as well as provided in a listing. The TG lowering medication will be identified as post-randomization concomitant medications with indication of 'hypertriglyceridemia'.

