15.3. ADDITIONAL POST-RANDOMIZATION LIPID MODIFYING THERAPY

The number and percent of patients in each treatment group requiring additional (post-randomization) lipid-lowering therapy will be summarized by treatment group, ATC class 4 and medication name as well as provided in a listing. The lipid-lowering therapy includes all post-randomization concomitant medications based on ATC class 2 = lipid-modifying agent.

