17.3.3. ANALYSIS OF TERTIARY EFFICACY VARIABLES

Tertiary efficacy endpoints of LDL-C, non-HDL-C, TC and ApoB will be analyzed using the same ANCOVA model described in [17.1.2](#). Each statistical comparison will be conducted at significant level of 0.05.

hsCRP will be analysed using non-parametric Wilcoxon rank sum test as described in [17.2.1](#).

In addition, the LDL-C endpoint at week 52 will be analyzed with patients in the FAS who did not receive additional lipid-lowering therapy by that time point (by week 52). Only observed case data will be used (no imputation for missing data).

For endpoint of HDL-C and TG at week 12, 24, and 52 summary statistics will be provided for actual value, change and percent change at each visit by treatment group.

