APPENDIX 2. PARTIAL DATE CONVENTIONS

Imputed dates will NOT be presented in the listings.

Algorithm for Treatment Emergence of Adverse Events:

START DATE	STOP DATE	ACTION
Known	Known	If start date < study med start date, then not TEAE If start date >= study med start date and <=study med end date + 30, then TEAE
	Partial	If start date < study med start date, then not TEAE If start date >= study med start date and <=study med end date + 30, then TEAE
	Missing	If start date < study med start date, then not TEAE If start date >= study med start date and <=study med end date + 30, then TEAE
Partial, but known components show that it cannot be on or after study med start date	Known	Not TEAE
	Partial	Not TEAE
	Missing	Not TEAE
Partial, could be on or after study med start date	Known	If stop date < study med start date, then not TEAE If stop date >= study med start date and <=study med end date + 30, then TEAE
	Partial	Impute stop date as latest possible date (i.e. last day of month if day unknown or 31st December if day and month are unknown), then: If stop date < study med start date, then not TEAE If stop date >= study med start date and <=study med end date + 30, then TEAE
	Missing	Assumed TEAE
Missing	Known	If stop date < study med start date, then not TEAE If stop date >= study med start date and <=study med end date + 30, then TEAE
	Partial	Impute stop date as latest possible date (i.e. last day of month if day unknown or 31st December if day and month are unknown), then: If stop date < study med start date and <=study med end date + 30, then not TEAE

Statistical Analysis Plan

START DATE	STOP DATE	ACTION
		If stop date >= study med start date and <=study med end date + 30, then TEAE
	Missing	Assumed TEAE

Algorithm for Prior / Concomitant Medications:

START DATE	STOP DATE	ACTION
Known	Known	If stop date < study med start date, assign as prior If stop date >= study med start date and start date <= end of treatment, assign as concomitant If stop date >= study med start date and start date > end of treatment, assign as post study
	Partial	Impute stop date as latest possible date (i.e. last day of month if day unknown or 31 st December if day and month are unknown), then: If stop date < study med start date, assign as prior If stop date >= study med start date and start date <= end of treatment, assign as concomitant If stop date >= study med start date and start date > end of treatment, assign as post treatment

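### The SAP's added-therapy counts rest on two conflicting definitions of concomitant medication, and lipid therapy started more than 30 days after study drug is stopped is missed under both

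*SAP*

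**What the plan says.** SAP Section 15 (Medications) includes as concomitant a drug that "started no later than 30 days following end of study medication".

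SAP Appendix 2, in the algorithm for prior and concomitant medications, uses an earlier limit. Its first row, for fully known start and stop dates, reads "If stop date >= study med start date and start date <= end of treatment, assign as concomitant" and then "If stop date >= study med start date and start date > end of treatment, assign as post study". Later rows call the second group *post treatment*. Because the rule covers complete dates, it is more than a convention for partial ones. *End of treatment* is not defined, and nothing says whether Section 15 or Appendix 2 prevails.

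The counts of added therapy depend on this status. SAP 15.3: "The lipid-lowering therapy includes all post-randomization concomitant medications based on ATC class 2 = lipid-modifying agent". SAP 15.2 does the same for triglycerides: "The TG lowering medication will be identified as post-randomization concomitant medications with indication of 'hypertriglyceridemia".

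SAP 17.3.3 adds a Week 52 LDL-C analysis restricted to FAS patients "who did not receive additional lipid-lowering therapy by that time point (by week 52"). It gives no rule for identifying them and does not mention concomitant status.

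Protocol 12.7 promises the number and percentage of patients needing added LDL-C or triglyceride therapy after randomization, with no limit tied to IMP. Under protocol 10.3.1, patients who stop IMP are asked to keep attending visits with fasting lipids. Those who will only take phone calls are still asked about concomitant medications.

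**The concern.** A count of therapy added after randomization should not depend on whether the patient is still taking study drug. Here it does, through the word *concomitant*, and the SAP gives that word two meanings. The same data therefore yield different tables according to which rule is programmed, and both tables omit later starts.

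The patients affected are foreseeable. Protocol 11.1.6.4.1 takes patients off IMP when the investigator judges that they need prohibited lipid therapy, and 11.1.6.4.2 does so for persistent triglyceride elevation. Their later lipid values and their new drug can both be in the database while the table shows no added therapy. Protocol 12.1 lets the SAP supersede the protocol, so the narrower SAP definition would govern.

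The second stake is conditional. SAP 15.3 is the only place where added lipid-lowering therapy is defined, so a programmer could well reuse it for 17.3.3. Patients who had in fact started another agent off IMP would then remain in an analysis meant to exclude them.

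**Working it through.** **Inputs.** Start limits come from SAP Section 15 and Appendix 2. Visit target days 85, 168, 252 and 365 come from SAP 6.4, and the 750 patients from SAP 7.1. *End of treatment* is taken as the last dose, an assumption because the term is undefined. The plan states no figure for added therapy, so there is none to reproduce.

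**Step 1. Classify a new lipid agent by its start date relative to the last dose.**

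| Start date | Section 15 | Appendix 2 | Counted in 15.3? |
|---|---|---|---|
| On or before last dose | concomitant | concomitant | yes |
| 1 to 30 days after | concomitant | post treatment | depends on the rule used |
| 31 or more days after | not concomitant | post treatment | no |

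For example, a patient who stops on Day 20 and starts ezetimibe on Day 55 has a gap of 55 − 20 = 35 days and is counted under neither rule.

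Appendix 2 also treats undated drugs more generously than dated ones. With a missing start date and a stop date on or after the start of study medication, or no stop date, the drug is concomitant. A documented start after IMP is dropped, while an undated one is counted.

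**Step 2. Days on which a start would be missed.** With IMP stopped on day *s*, days to Week 52 = 365 − *s*. Section 15 misses (365 − *s*) − 30; Appendix 2 misses all of them.

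| IMP stopped | Days to Day 365 | Missed, Section 15 | Missed, Appendix 2 |
|---|---|---|---|
| Day 85 | 280 | 250 (89.3%) | 280 |
| Day 168 | 197 | 167 (84.8%) | 197 |
| Day 252 | 113 | 83 (73.5%) | 113 |

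These are shares of calendar time. They are not shares of patients.

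**Step 3. Illustrative patient counts, on assumed rates.** The documents give no rate of stopping IMP and no share starting another agent afterwards. Suppose 10% to 30% stop and 5% to 20% of those later start one:

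- Low: 750 × 0.10 × 0.05 = 3.75. High: 750 × 0.30 × 0.20 = 45. Appendix 2 misses all of them, about 4 to 45.
- Section 15, if all stop on Day 168 and start times are uniform to Day 365: multiply by 167/197, giving about 3 to 38.

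**Step 4. Week 52 analysis, only if the 15.3 definition is reused.** The shift in the treatment difference is (*f* bempedoic acid − *f* placebo) × *e*. Here *f* is the fraction wrongly kept in each arm and *e* the added agent's effect on percent change in LDL-C. All values are assumed.

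- 1% versus 3%, *e* = −15: (0.01 − 0.03) × (−15) = +0.3 points.
- 2% versus 5%, *e* = −50: (0.02 − 0.05) × (−50) = +1.5 points.
- With the arms exchanged the signs reverse: −0.3 and −1.5. With equal fractions the shift is 0.

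**The case against.** Much of the defence stands.

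- A reader might infer that all lipid therapy started after IMP falls outside both rules. It does not: starts within 30 days are concomitant under Section 15. If starts cluster soon after stopping, that rule catches many of them.
- A reader might infer that treated patients do remain in the Week 52 analysis. The wording of 17.3.3 does not say so. It excludes anyone who received added therapy by Week 52 and does not cite 15.3. Read literally, it is right.
- A reader might object that these patients' lipids stay in the FAS. That is intended: SAP 5.2 and 17.1.2 analyse everyone as randomized, whatever they took.
- The sensitivity analysis in SAP 17.2.3.2 keeps only laboratory results dated up to the LMT change, with no concomitant condition. It already handles the primary and key secondary endpoints, and a patient-level flag could discard valid results from before the change.
- Under protocol 11.1.6.4.1, background therapy is adjusted first, while the patient is on IMP. Those changes count under both rules.
- One could read *end of treatment* as the end of the planned 52 weeks, which would make Appendix 2 the wider rule. The text does not settle this. The two rules would still disagree.

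What does not fall away is the conflict itself and the link in 15.2 and 15.3 to concomitant status.

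**Conclusion.** The point holds within limits. The two cut-offs conflict on the face of the SAP. With *end of treatment* read as last dose, therapy started more than 30 days after IMP is stopped is missed under both, and from the first day under Appendix 2. The added-therapy tables therefore under-count relative to protocol 12.7. This is a stated rule that gives a wrong count, so it is more than missing detail.

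The Week 52 consequence arises only if the 15.3 definition is carried into 17.3.3. It would touch one unimputed analysis of a tertiary endpoint outside the testing hierarchy. The primary and key secondary FAS analyses, and the date-based 17.2.3.2 analysis, are not affected on the text.

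The patient counts and the 0.3 to 1.5 point range are illustrations on assumed inputs. Actual size and direction cannot be computed from the documents. A shift in one arm's mean should not be read as bias in the treatment difference, since only the imbalance between arms matters.

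**What to change.** 1. Use one concomitant window in Section 15 and Appendix 2, and define *end of treatment*.
2. In 15.2 and 15.3, identify added therapy by a start or dose-increase date after randomization and up to the last study visit, regardless of IMP status. Keep the existing ATC class and indication criteria.
3. In 17.3.3, apply that definition up to the date of the Week 52 visit.
4. Leave the date rule in 17.2.3.2 as it is.

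The cost is a few sentences in the SAP. The protocol already has medications recorded with start and stop dates, and lipid-therapy changes with their start dates, so no new data are needed. The December 2018 addendum reports the planned analyses as completed. For existing outputs, state which window was programmed and, where it was tied to IMP, rerun the added-therapy tables and, if the 15.3 definition was used there, the Week 52 analysis.
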